2.8.1.1 Deaths

Separate summary and listing will be provided for deaths.

2.8.2 Laboratory data

2.8.2.1 Hematology and clinical chemistry

Similar to AEs, the laboratory data will be summarized and presented by treatments for the SAF. The summary of laboratory evaluations will include 2 groups of laboratory tests (hematology and clinical chemistry).

- All the summary of lab outputs (newly occurring notables, maximum changes, shift tables, by visit summary statistics) will consider the "on-treatment" data. i.e., all assessments within last dose plus 84 days.

Follow up visit summary: Summary of follow up visit outputs may be provided if required. The listing will provide follow up visit records.

- All records are displayed in the listing with the on-treatment flag. i.e., occurred within last dose plus 84 days- yes or no, as well as eCRF visits and phase.

Descriptive summary statistics for the change from Baseline to each study visit will be presented by test group, laboratory test, and treatment arm. Change from Baseline will only be summarized for subjects with both Baseline and post-Baseline data. For each parameter, the maximum change from Baseline within each study phase will be analyzed analogously.

change from baseline = post baseline value – baseline value

In addition, shift tables will be provided for all parameters to compare a subject's baseline laboratory evaluation relative to the most extreme laboratory test value within a treatment period. For the shift tables, the normal laboratory ranges will be used to evaluate whether a particular laboratory test value was normal, low, or high (including category "high and low"). These summaries will be presented by laboratory test and treatment arm. The following laboratory parameters will be analyzed with respect to numerical Common Terminology Criteria for Adverse Events (CTCAE) grades, given in Table 2-5: hemoglobin, platelets, white blood cell count, neutrophils, lymphocytes, creatinine, total bilirubin (TBL), alkaline phosphatase (ALP), glucose, cholesterol, triglycerides (TG).

The number and percentage of subjects with CTCAE grade newly occurring or worsening after baseline will be presented for each parameter by treatment and analysis phase. These summaries will be split into hematology and chemistry for study level reports and the pooled summary of clinical safety.

Table 2.5 CTCAE grades for laboratory parameters to be analyzed

CTCAE v4.0 Term	Grade 1	Grade 2	Grade 3	Grade 4
HGB decreased (Anemia)	< LLN - 100 g/L	< 100 - 80 g/L	< 80 g/L	Life-threatening consequences; urgent intervention
Platelet count	< LLN – 75.0 x10e9 /L	< 75.0 - 50.0 x10e9 /L	< 50.0 – 25.0 x10e9 /L	< 25.0 x 10e9 /L

CTCAE v4.0 Term	Grade 1	Grade 2	Grade 3	Grade 4
decreased				
White blood cell decreased	< LLN - 3.0 x 10e9 /L	< 3.0 - 2.0 x 10e9 /L	< 2.0 - 1.0 x 10e9 /L	< 1.0 x 10e9 /L
Neutrophil count decreased	< LLN - 1.5 x 10e9 /L	< 1.5 - 1.0 x 10e9 /L	< 1.0 - 0.5 x 10e9 /L	< 0.5 x 10e9 /L
Lymphocyte count decreased	< LLN - 0.8 x 10e9/L	< 0.8 - 0.5 x 10e9 /L	< 0.5 - 0.2 x 10e9 /L	< 0.2 x 10e9 /L
Creatinine increased*	> 1 - 1.5 x baseline; > ULN - 1.5 x ULN	> 1.5 - 3.0 x baseline; > 1.5 - 3.0 x ULN	> 3.0 baseline; > 3.0 - 6.0 x ULN	> 6.0 x ULN
TBL increased	> ULN - 1.5 x ULN	> 1.5 - 3.0 x ULN	> 3.0 - 10.0 x ULN	> 10.0 x ULN
GGT increased	> ULN - 2.5 x ULN	> 2.5 - 5.0 x ULN	> 5.0 - 20.0 x ULN	> 20.0 x ULN
ALP increased	> ULN - 2.5 x ULN	> 2.5 - 5.0 x ULN	> 5.0 - 20.0 x ULN	> 20.0 x ULN
Glucose increased (Hyperglycemia)	; > ULN - 8.9 mmol/L	> 8.9 - 13.9 mmol/L	> 13.9 - 27.8 mmol/L	> 27.8 mmol/L
Glucose decreased (Hypoglycemia)	<LLN - 3.0 mmol/L	< 3.0 - 2.2 mmol/L	< 2.2 - 1.7 mmol/L > 10.34 - 12.92 mmol/L	< 1.7 mmol/L > 12.92 mmol/L
Cholesterol high	> ULN - 7.75 mmol/L	> 7.75 - 10.34 mmol/L	> 10.34 - 12.92 mmol/L	> 12.92 mmol/L
Hypertriglyceridemia	1.71 - 3.42 mmol/L	> 3.42 - 5.7mmol/L	> 5.7 - 11.4 mmol/L	> 11.4 mmol/L

*Note: for "creatinine increased" the baseline criteria do not apply

Shift tables will be presented comparing baseline laboratory result (CTCAE grade) with the worst results (expressed in CTCAE grade) during the treatment phase (either first or entire) analyzed. Of note, baseline will be defined as last assessment prior to first dosing in initial treatment phase. Subjects with abnormal laboratory values will be listed and values outside the normal ranges will be flagged. The number and percentage of subjects with clinically CTCAE grade newly occurring or worsening after baseline will be presented. The expanded laboratory ranges and the clinically notable abnormalities of key laboratory variables are given in [Table 2-6](#). Number and percentages of subjects with notable lab values will be summarized by treatment as well as listed.

Table 2-6 Criteria for notable abnormalities

Liver function and related variables	
Total bilirubin	> 2 x ULN
Alkaline phosphatase	> 2.5 x ULN
Renal function and electrolyte variables	
Creatinine (serum)	> 1.5 x ULN
Potassium	> 6 mmol/L or < 3 mmol/L
Sodium	> 160 mmol/L or < 115 mmol/L
Urinalysis variable	
Protein urine dipstick	2+ (100 mg/dL)
Hematology values	
Hemoglobin	≥ 20 g/L decrease from Baseline
Platelet count	< Lower Limit of Normal (LLN)
White blood cell count	< 0.8 x LLN
Neutrophils	< 0.9 x LLN
Eosinophils	> 1.1 x ULN
Lymphocytes	> 1.1 x ULN

Individual subject data listings will be provided for subjects with newly occurring or worsening abnormal laboratory data.

Visit wise count and percentage and listing will be produced for urinalysis - local lab result parameters.

2.8.3 Other safety data

2.8.3.1 ECG data

Data collected in “12 Lead ECG Evaluation – Local” eCRF page will be listed.

2.8.3.2 Vital signs

Vital sign measurements will be analyzed using summary statistics for the change from Baseline along with their absolute values for each post-Baseline visit and presented by vital sign and treatment arm. Change from Baseline will only be summarized for subjects with both Baseline and post-Baseline values.

Change from baseline will only be summarized for subjects with both baseline and post-baseline values and will be calculated as:

$$\text{change from baseline} = \text{post-baseline value} - \text{baseline value}$$

Only “on-treatment” vital signs will be summarized (i.e. assessments within last dose plus 84 days). All vital signs will be listed with “on-treatment” flag displayed.

The criteria for notable vital sign abnormalities are given in [Table 2.8](#). The number and percentage of subjects with newly occurring notable vital signs will be presented. A listing of subjects with newly occurring notably abnormal vital signs will be provided.

Table 2-8 Criteria for notable vital sign abnormalities

Vital signs (unit)	Normal measure	Notable abnormality
Systolic blood pressure (mmHg)	90 to < 120 mmHg	>= 140 mmHg (hypertension) or < 90 mmHg (hypotension)
Diastolic blood pressure (mmHg)	60 to < 80 mmHg	>= 90 mmHg (hypertension) or < 60 mmHg (hypotension)
Pulse (bpm)	60 to 100(bpm)	> 100 bpm (tachycardia) or < 60 bpm (bradycardia)

Note: A blood pressure indicative of prehypertension (systolic blood pressure of 120 to < 140 mmHg and/or diastolic blood pressure of 80 to < 90 mmHg) will not be regarded as notable (Chobanian, Bakris, and Black 2003).

A listing of the newly-occurring notably abnormal vital signs will be provided. “Vital sign” eCRF page will be used to get this information.

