- **Arm B1:** patients with new-onset plaque psoriasis will receive 1 or 2 cycles of nb-UVB of 12 weeks each with a maximum break of 28 weeks between cycles (patients with PASI 90 at Week 40 will not receive a second treatment cycle). Only during the first 4 weeks of each cycle, nb-UVB treatment may be given in combination with topical calcipotriol 50 µg/g and betamethasone 0.5 mg/g

Follow-up Epoch

At the end of the Treatment Epoch at Week 52, all patients with \geq PASI 50 response from Arm A1 and Arm B1 will enter the Follow-up Epoch. Patients who do not achieve a PASI 50 response, will have all assessments of EOS and be discontinued from the study.

During the Follow-up Epoch, patients will not receive study treatment; they will be observed maximally until Week 208, and compared regarding the proportion of them who achieve PASI 90 scores at Week 104.

[figure not shown]
Patients who relapse (those who experience a loss of 50% of the maximum improvement in PASI score achieved during the Treatment Epoch) will have all assessments of EOS and be discontinued from the study.

If no relapse occurs, patients who achieve $<$ PASI 90 at Week 52 in Arms A1 (A1a and A1b) and B1 (B1a and B1b) will be followed (according to the visit schedule outlined in [Table 6-3](#))

until Week 104, while patients who achieve \geq PASI 90 at Week 52 will be followed until Week 208.

The investigator should provide ongoing adequate care for patients who relapse. If the investigator decides to continue treating the patients with secukinumab, a new loading dose of commercially available secukinumab could be considered. The treatment with secukinumab after relapse will be out of scope of the study.

Figure 3-1 Study design – Main Study

BL = baseline, EOS = end of study, KSE = key secondary endpoint, nb-UVB=narrow-band ultraviolet B, PASI = psoriasis area and severity index, PE = primary endpoint, R = randomization.

Mechanistic Sub-study

A separate informed consent will be obtained from study patients who agree on having skin biopsies taken and therefore become eligible for this Mechanistic Sub-study. Besides the biopsies, patients will undergo the same assessments as in the Main Study.

Treatment Epoch

At the baseline visit, eligible patients will be allocated to one of the treatment arms of the Mechanistic Sub-study (see [Figure 3-1](#) and [Section 5.3](#)):

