9.5.3 Safety variables

All safety evaluations will be performed on the SAF.

For the Main Study, the safety of secukinumab compared with nb-UVB will be evaluated. For the Mechanistic Sub-study, similar safety evaluations will be performed by treatment and study epoch.

Adverse events

Treatment emergent AEs (events started after the first dose of study treatment or events present prior to the first dose of study treatment but increased in severity based on preferred term) will be summarized. Only primary paths within MedDRA will be considered for AE reporting.

Adverse events will be summarized by presenting, for each treatment arm, the number and percentage of patients having any AE, having an AE in each primary system organ class and having each individual AE (preferred term). Summaries will also be presented for AEs by severity and for study treatment related AEs. If a patient reported more than one AE with the same preferred term, the AE with the greatest severity will be presented. If a patient reported

more than one AE within the same primary system organ class, the patient will be counted only once with the greatest severity at the system organ class level, where applicable.

Separate summaries will be provided for psoriatic arthritis, death, SAEs, other significant AEs leading to discontinuation from the study, and AEs leading to study treatment discontinuation. In addition, exposure adjusted summaries including 95% confidence intervals for the occurrence rate of AEs in 100 patient years will be provided by treatment.

Laboratory data

The summary of laboratory evaluations will be presented for 2 groups of laboratory tests (hematology and clinical chemistry). Descriptive summary statistics for the changes from baseline to each study visit will be presented by test group, laboratory test, and treatment arm. Changes from baseline will only be summarized for patients with both baseline and post-baseline data.

For each parameter, the maximum change from baseline within each study epoch will be analyzed analogously.

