2.1.1.4 Day of last dose of randomized study treatment

The date of last dose will be collected via the eCRF. The subject's exposure will be calculated considering the last visit or the last dose + 84 days whichever occurs earlier.

For safety analysis on-treatment is defined as assessments from the first dose to last dose plus 84 days.

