Compliance for secukinumab is defined as actual cumulative dose divided by cumulative assigned dose. Treatment compliance for subjects will be summarized for subjects for 16 weeks, 52 weeks and for A2 104 weeks.

nb-UVB

Subjects in B1a and B1b receive nb-UVB.

The number of sessions in Cycle 1 and Cycle 2 will be categorized into < 24, 24-36 and count in each category will be presented, number of subjects exposed to treatment with nb-UVB to whole body or partial body will also be summarized. The number of subjects required a second cycle also will be presented.

On-treatment exposure to the study treatment will be defined (in days) time (from first dose to the time to the last dose of treatment+84) . Duration of exposure in Cycle 1 and Cycle 2 will be summarized.

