2.8 Safety analyses

All safety evaluations will be performed on the SAF

In general, the following guidelines are proposed for safety analysis:

- Adverse events: Only treatment emergent records are reported in the tables, and listings have the “treatment emergent” flag displayed.
- Other safety data (e.g. laboratory data, vital sign, ECG, Physical examination etc):
 - by visit summary statistics tables: only include “on-treatment” records in the tables, i.e., assessments within last dose plus 84 days cutoff. Listings have the “on-treatment” flag displayed. Follow up visits (eCRF visits) may be summarized separately if required.

For the Main Study, the safety of secukinumab compared with nb-UVB will be evaluated. For the Mechanistic Sub-study, similar safety evaluations will be performed by treatment and study phase.

Entire treatment/study period for Main study (A1a+A1b and B1a+B1b)

Entire treatment period = randomization to Week 52 (EOT); for safety analysis include FU period up to last dose + 84 days.

Entire study period = randomization to end of study (EOS); includes follow up period (Week 208)

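### The last-dose-plus-84-days filter drops single-cycle nb-UVB patients from the Week 36 and Week 52 laboratory and vital-sign tables, leaving Arm B1 there as a post-randomization subset

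*SAP*

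**What the plan says.** SAP 2.1.1.4 sets the general rule: "For safety analysis on-treatment is defined as assessments from the first dose to last dose plus 84 days". SAP 2.4.1 writes the same formula for phototherapy: "On-treatment exposure to the study treatment will be defined (in days) time (from first dose to the time to the last dose of treatment+84" days.

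Three safety sections use this rule as a filter:

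- SAP 2.8 admits to the by-visit tables only on-treatment "records in the tables, i.e., assessments within last dose plus 84 days cutoff".
- SAP 2.8.2.1 extends it beyond the by-visit tables. "All the summary of lab outputs (newly occurring notables, maximum changes, shift tables, by visit summary statistics) will consider the" on-treatment data, defined there as "all assessments within last dose plus 84 days".
- SAP 2.8.3.2 says that only on-treatment "vital signs will be summarized (i.e. assessments within last dose plus 84 days", just after promising summaries at every visit after baseline.

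Protocol 9.5.3 has no such limit. For laboratory data, "Descriptive summary statistics for the changes from baseline to each study visit will be presented"; for vital signs it plans a summary at each visit after baseline.

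Protocol 3.1 explains why the last session varies so much within Arm B1: "patients with PASI 90 at Week 40 will not receive a second treatment cycle". Each cycle lasts 12 weeks, and 28 weeks is the longest break allowed between cycles.

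SAP 2.8 also defines the entire treatment period of the main study as randomization to Week 52 and, for safety, adds follow-up to 84 days after the last dose.

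**The concern.** Protocol Table 6-1 schedules laboratory tests and vital signs at Weeks 16, 24, 36 and 52 in all arms. The Week 36 and Week 52 values of a single-cycle B1 patient are therefore planned and collected. Whether they enter the tables depends on when phototherapy ended, and that depends largely on how the patient responded after randomization.

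Protocol 9.5.3 says that the safety of secukinumab will be compared with that of nb-UVB. At Weeks 36 and 52 the A1 column would hold essentially all treatment completers, and the B1 column mainly patients who needed a second cycle. A trend over visits in B1 could then reflect a change in who is summarized. Exposure-adjusted event rates do not help, because the problem lies in which measured values enter a by-visit mean.

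The SAP also conflicts with itself. In its definition of the treatment period the 84 days extend a 52-week period; in the table rules they shorten it.

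**Working it through.** **Plan's own figures.** SAP Table 2-1 uses day = 7 × week + 1, which gives Days 113, 169, 253 and 365 for Weeks 16, 24, 36 and 52, and Day 449 for Week 64. The upper window limit is the scheduled day plus half the gap to the next visit: 113 + 28 = 141; 169 + 42 = 211; 253 + 56 = 309; 365 + 42 = 407. All four match the table for A1 and B1. The Week 24, 36 and 52 windows open on Days 142, 212 and 310.

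**Rule.** Cut-off = day of last dose or session + 84.

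**Arm A1 completer.** The last dose at Week 48 is Day 337, and 337 + 84 = 421. This is later than Day 407, so every visit to Week 52 is kept.

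**Arm B1, one cycle.**

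| Cycle | Last session | Cut-off | Week 24 (Day 169) | Week 36 (from Day 212) | Week 52 (from Day 310) |
|---|---|---|---|---|---|
| On schedule | Day 78-85 | Day 162-169 | borderline | out | out |
| 2 weeks longer | Day 92-99 | Day 176-183 | in | out | out |
| 4 weeks longer | Day 106-113 | Day 190-197 | in | out | out |

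Protocol 5.5.5 allows up to 2 weeks between consecutive sessions; the 4-week row is a stress test. A Week 24 visit on schedule needs a last session on or after Day 169 - 84 = 85. No plausible single cycle reaches the first day of the Week 36 window.

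**Arm B1, two cycles.** With a break of b weeks, cycle 2 starts at Week 12 + b and the last day is 7 × (24 + b).

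| Break | Cycle 2 starts | Last day | Cut-off | Week 36 (Day 253) | Week 52 (Day 365) |
|---|---|---|---|---|---|
| 0 weeks | Week 12 | 168 | 252 | borderline | out |
| 15 weeks | Week 27 | 273 | 357 | in | out |
| 16 weeks | Week 28 | 280 | 364 | in | borderline |
| 17 weeks | Week 29 | 287 | 371 | in | in |
| 28 weeks | Week 40 | 364 | 448 | in | in |

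A Week 52 visit on schedule therefore needs a last session on or after Day 365 - 84 = 281, which means that cycle 2 starts at about Week 28 or later.

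**Patients left in B1.** If s is the single-cycle share, at most 80 × (1 - s) B1 patients can contribute at Weeks 36 and 52, before dropout. The documents do not give s. Assumed values: s = 0.20 leaves 64; s = 0.35 leaves 52; s = 0.50 leaves 40. The middle value equals the planned B1 PASI 90 rate at Week 52, but that rate follows one or two cycles and does not measure s.

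**The case against.** An on-treatment restriction is a normal choice for safety summaries, and 84 days matches the 12-week window for serious adverse events in Protocol 7.2.2. The tables are descriptive. The protocol says each visit, but it does not add regardless of last dose. SAP 2.8 and 2.8.2.1 also allow separate follow-up summaries if required. All of this is true and limits the consequence. It does not remove the problem. Weeks 36 and 52 are Treatment Epoch visits in Protocol Table 6-1, follow-up visits begin at Week 64 in Table 6-3, and an optional summary or a listing does not restore the comparison between arms.

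A reader might infer more than the documents support:

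- **That the values are deleted.** They are not. SAP 2.8.2.1 and 2.8.3.2 list all records with a flag.
- **That the remaining B1 patients are all cycle-1 non-responders, none with PASI 90 at Week 40.** A patient may respond to cycle 1, lose the response by Week 40 and receive cycle 2. As 28 weeks is only the maximum break, cycle 2 may also start before Week 40. Conversely, some single-cycle patients will have stopped for the other reasons in Protocol 5.6.2.
- **That record coverage can be fixed at one visit in four for single-cycle and four in four for two-cycle patients.** Week 24 turns on one day, and Week 52 after two cycles depends on the break.
- **That the A1 column holds every A1 patient still attending.** The filter also removes late visits of A1 patients who stopped treatment early.
- **That this is an undeclared change from the protocol.** The visible text of SAP section 4 does not mention it, but parts of that section are redacted.

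**Conclusion.** The concern holds for the summary tables. As written, the filter leaves single-cycle B1 patients out of the scheduled Week 36 and Week 52 summaries, and patients with an early second cycle out of Week 52. A1 completers stay in throughout. The B1 columns at those visits are selected after randomization, largely by response, and should not be read against A1.

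The timing result rests on a 12-week cycle starting near Day 1 and survives a 4-week extension. The patient counts rest on the assumed single-cycle share and are upper limits. SAP 2.4.1 plans to report how many patients needed a second cycle, so the actual share will be known. The direction and size of any effect on laboratory or vital-sign means cannot be derived from the documents. No hypothesis test is affected. The change should be made because the comparison is a stated safety aim and the SAP's own definitions need reconciling.

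**What to change.** In SAP 2.8, 2.8.2.1 and 2.8.3.2, for Arms A1 and B1, base the by-visit laboratory and vital-sign tables on all records from first dose to the later of the Week 52 visit and last dose plus 84 days. Use the same record set for the notable-value, maximum-change and shift outputs, which now share the filter; otherwise the safety outputs would rest on different records. Align the wording with the treatment-period definition in SAP 2.8. Keep the strict on-treatment version as supportive and the flag in the listings.

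The cost is a few sentences and one changed filter; any tables already produced would need a rerun. The data are already scheduled for collection. The small downside is that some B1 values will lie more than 12 weeks after the last session, which a footnote should state.

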2.9 Pharmacokinetic endpoints

[figure not shown]
Not Applicable.

[figure not shown]
2.10 Skin Biopsy

[figure not shown]
Skin biopsies will be collected from subjects participating in the mechanistic sub-study as per the schedule defined in [Table 1-2](#) in Study design section. SAF will be used for the analysis.

Punch biopsies from lesional or resolved skin (2 biopsies, 4 millimeters in diameter) and never-lesional skin (1 biopsy, 3 millimeters in diameter) will be taken according to the schedule shown in [Table 2-2](#), and transported to Karolinska Institute, Stockholm, Sweden. Biopsy 1 from lesional or resolved skin (4 millimeters in diameter) sample will be used for gene expression analysis and Biopsy 2 from lesional or resolved skin (4 millimeters in diameter) and never-lesional skin (1 biopsy, 3 millimeters in diameter) will be used for histology analysis.

Skin biopsies will be taken from subjects in Arm A1b, Arm A2, Arm B1b, Arm C1, and Arm C2 to assess the total number of T_{rm} cells and subsets of these cells, especially those capable of producing IL-17A and IL-22 inflammatory mediators considered to be vital to maintain subclinical inflammation.

[figure not shown]

[figure not shown]

[figure not shown]

[figure not shown]
2.13 Other Exploratory analyses

[figure not shown]

[figure not shown]

[figure not shown]

